3.1 Overall Study Design and Plan

This is a randomized, double-blind, placebo-controlled, multicenter, parallel-group study to evaluate the efficacy and safety of nemolizumab in adult subjects with moderate to severe CKD-aP.

Subjects will be randomized in one of the following three arms/groups (two different doses of nemolizumab and a placebo) in a 1:1:1 ratio:

[figure not shown]
- Group 1: 30 mg Nemolizumab Q4W with a 60 mg loading dose at baseline;
- Group 2: 60 mg Nemolizumab Q4W without loading dose at baseline;
- Group 3: Placebo Q4W.

Approximately 84 subjects will be randomized in each nemolizumab group and in the placebo group for a total sample size of approximately 252 subjects.

In order to maintain the blind, all subjects will receive 2 injections at each administration (30 mg + 30 mg or 30 mg + placebo or placebo + placebo).

The study consists of a screening period (up to 4 weeks), a 12-week treatment period, and an 8-week follow up period (12 weeks after the last study drug injection). The screening period will evaluate subject eligibility. At the baseline visit, subjects will receive an initial dose of nemolizumab 60 mg or placebo by two subcutaneous (SC) injections (30 mg + 30 mg, or placebo + placebo). Study drug treatment with either nemolizumab or placebo should start after completion of the hemodialysis treatment (within four hours). Then study drug (i.e., nemolizumab 30 mg, nemolizumab 60 mg or placebo) will be administered via two SC injections (30 mg + placebo, 30 mg + 30 mg, or placebo + placebo) at Week 4 and Week 8 after completion of hemodialysis treatment (within four hours). **CCI** [REDACTED] are to be taken before hemodialysis. [Figure 1](#) below presents the study design:

Figure 1

R = Randomization; * = Visits with study drug administration

Note: All subjects in each arm will receive 2 injections at each administration (either 30 mg + 30 mg, or 30 mg + placebo, or placebo + placebo) in order to maintain the blind

The schedule of assessments is summarized in [Appendix A](#).

3.2 Study Endpoints

3.2.1 Primary Efficacy Endpoint

[figure not shown]
The primary efficacy endpoint is the proportion of subjects with an improvement of Worst Itch Numeric Rating Scale (WI NRS) ≥ 4 from baseline at Week 12 without use of rescue therapies and without treatment discontinuation due to lack of efficacy or AE/death related to study drug. Subjects who took rescue therapies or discontinued treatment due to lack of efficacy or AE/death related to study drug will be considered treatment failures (see [Table 6](#) for full details of the primary estimand). Note that this combines the outcome with intercurrent events by defining a binary composite response.

3.2.2 Secondary Efficacy Endpoints

[figure not shown]
The key secondary efficacy endpoints are defined as follows:

1. Proportion of subjects with an improvement of WI NRS ≥ 3 from baseline at Week 12.
2. Proportion of subjects with an improvement of WI NRS ≥ 4 from baseline at Week 4.
3. Proportion of subjects with an improvement of Sleep Disturbance Numeric Rating Scale (SD NRS) ≥ 4 from baseline at Week 12.
4. Proportion of subjects with an improvement of WI NRS ≥ 3 from baseline at Week 4.
5. Proportion of subjects with an improvement of SD NRS ≥ 4 from baseline at Week 4.

CCI

CCI

3.2.6 Other Safety Measurements

Other safety measurements are as follows:

1. Physical examination and vital signs.
2. Clinical laboratory tests.

3. Electrocardiogram (ECG) results.
4. Respiratory examination and assessments.

3.3 Treatments

This study has three treatment arms at a ratio of 1:1:1. Subjects will receive a loading dose of nemolizumab (60 mg) or Placebo by two SC injections at baseline (30 mg + 30 mg, placebo + placebo) and a 30 mg or 60 mg dose of nemolizumab or placebo by two SC injections (30 mg + placebo, 30 mg + 30 mg, placebo + placebo) at Week 4 and at Week 8. All the study drug treatment should be performed following the completion of the hemodialysis treatment (within four hours). Table 1 below summarizes the study drug dosing during the treatment period of the study.

Table 1 Treatment Period Dosing by Treatment Group

Group	Treatment	Dose at Day 1/Baseline	Dose at Week 4 and Week 8	Route	Schedule
1	30 mg Nemolizumab (CD14152)	60 mg (two 30 mg injections)	30 mg (30 mg injection + placebo injection)	SC	Q4W
2	60 mg Nemolizumab (CD14152)	60 mg (two 30 mg injections)	60 mg (two 30 mg injections)	SC	Q4W
3	Placebo	Placebo (two placebo injections)	Placebo (two placebo injections)	SC	Q4W

Abbreviation(s): Q4W = every four weeks; SC = subcutaneous.

4 General Statistical Considerations

All summaries and results in Tables, Listings and Figures (TLFs) should be presented for the following groups:

Table 2 Treatment Group Labels in TLFs

Treatment Groups	Label in TLFs
60 mg loading dose of nemolizumab by two SC injections of 30 mg at Baseline, followed by one SC injection of 30 mg of nemolizumab + one SC injection of placebo at Week 4 and at Week 8	Nemolizumab 30 mg
Two SC injections of 30 mg of Nemolizumab at Baseline, at Week 4 and at Week 8	Nemolizumab 60 mg
Two SC injections of placebo at Baseline, at Week 4 and at Week 8	Placebo
Nemolizumab 30 mg, Nemolizumab 60 mg, and Placebo treatment groups combined	Total

The reference date for the calculation of study days will be the date of the first treatment injection on Day 1/Baseline for subjects randomized and treated or the date of randomization for subjects randomized but not treated (if any).

For events/assessments on or after the reference date, the study day of events/assessments is calculated as the date of event minus the reference date + 1. For events/assessments before the reference date, the study day of the events/assessments is calculated as the date of assessment minus the reference date.

Baseline is defined as the last non-missing measurement prior to the first treatment injection at Day 1/Baseline for subjects randomized and treated or prior to the randomization for subjects randomized but not treated (if any). Change from baseline and percent change from baseline are defined as follows:

$$\text{Change from Baseline} = \text{PostBaseline} - \text{Baseline}$$

$$\text{Percent Change from Baseline} = \begin{cases} \text{Baseline} \neq 0 \Rightarrow 100 \cdot \frac{\text{PostBaseline} - \text{Baseline}}{\text{Baseline}} \\ \text{Baseline} = 0 \Rightarrow \text{Missing} \end{cases}$$

All by-visit summaries and analyses will use the analysis visit (see section 4.10).

Continuous data will be summarized using the following descriptive statistics: number of subjects (n), mean, standard deviation (SD), median, first and third quartiles (Q1 and Q3), minimum and maximum. Categorical data will be summarized using the frequency count (n) and percentage (%) of subjects for each category. For the summary statistics of all numerical variables unless otherwise specified, minimum and maximum will be displayed to the same level of precision as reported. Mean, median, Q1 and Q3 will be displayed to one level of precision greater than the data collected. Standard deviation will be displayed to two levels of precision greater than the data collected.

P-values will be displayed in the following format, 0.9999. Any p-value less than 0.0001 will be displayed as <0.0001. Any p-value greater than 0.9999 will be displayed as >0.9999.

The following flagging conventions will be applied for the p-values of all statistical testing:

- $0.01 \leq p\text{-values} < 0.025$ will be flagged with one asterisk (e.g. “0.0249 *”).
- $0.001 \leq p\text{-value} < 0.01$ will be flagged with two asterisks (e.g. “0.0099 **”).
- $0.0001 \leq p\text{-value} < 0.001$ will be flagged with three asterisks (e.g. “0.0009 ***”).
- $p\text{-value} < 0.0001$ will be flagged with four asterisks (e.g. “<0.0001 ****”).

When count data are presented, the percentage will be suppressed when the count is zero in order to draw attention to the non-zero counts. The denominator for all percentages will be the number of subjects in that treatment within the analysis set of interest, unless otherwise specified. Percentages will be presented to one decimal place.

All proportions will be presented as percentages (not as fraction of unit).

Any imputed data will be used in analysis tables and figures (as applicable) and the original collected data will be used in summary tables and figures and displayed in listings.

Unless specified otherwise, all the summary tables will be presented overall and by treatment, and all the collected data will be presented in the listings. Data displayed in the listings will be sorted by treatment and subject identifier.

All analyses will be conducted using SAS Version 9.4 or higher.

4.1 Date Imputations

For the purpose of inclusion in prior and/or concomitant medication/procedure and AE tables, incomplete AEs and medications/procedures start and end dates will be imputed as follows:

- Start Date Imputation of Adverse Events:
 - Imputation of adverse event end date has to be done before imputation of event start date.
 - Completely missing: For subjects treated, impute to the date of first treatment injection. For subject randomized but not treated, impute to the date of randomization. For subjects not randomized, impute to the date of informed consent.
 - Missing day and month: For subjects treated, impute to January 1st, unless year is the same as year of first treatment injection then impute to the date of first treatment injection. For subject randomized but not treated, impute to January 1st, unless year is the same as year of randomization then impute to the date of randomization. For subjects not randomized, impute to January 1st, unless year is the same as year of informed consent then impute to the informed consent date.
 - Missing day: For subjects treated, impute to the 1st of the month, unless month and year are the same as month and year of first treatment injection then impute to the date of first treatment injection. For subject randomized but not treated, impute to the 1st of the month, unless month and year are the same as month and year of randomization then impute to the date of randomization. For subjects not randomized, impute to the 1st of the month, unless month and year are the same as month and year of informed consent then impute to the informed consent date.
 - If event end date (imputed or not) is not missing and imputed event start date is after event end date (imputed or not), set the event start date to the event end date (imputed or not).
- Start Date Imputation of Prior/Concomitant Therapies and Medical/Surgical Procedures:
 - Imputation of therapy/procedure end date has to be done before imputation of therapy/procedure start date.

- Completely missing: For subjects treated, impute to the date of first treatment injection. For subject randomized but not treated, impute to the date of randomization. For subjects not randomized, impute to the date of informed consent.
- Missing day and month: For subjects treated, impute to January 1st, unless year is the same as year of first treatment injection then impute to the date of first treatment injection. For subject randomized but not treated, impute to January 1st, unless year is the same as year of randomization then impute to the date of randomization. For subjects not randomized, impute to January 1st, unless year is the same as year of informed consent then impute to the informed consent date.
- Missing day: For subjects treated, impute to the 1st of the month, unless month and year are the same as month and year of first treatment injection then impute to the date of first treatment injection. For subject randomized but not treated, impute to the 1st of the month, unless month and year are the same as month and year of randomization then impute to the date of randomization. For subjects not randomized, impute to the 1st of the month, unless month and year are the same as month and year of informed consent then impute to the informed consent date.
- If therapy/procedure end date (imputed or not) is not missing and imputed therapy/procedure start date is after therapy/procedure end date (imputed or not), set the therapy/procedure start date to the therapy/procedure end date (imputed or not).
- Stop Date Imputation of Adverse Events, Prior/Concomitant Therapies and Medical/Surgical Procedures:
 - Completely missing and with outcome 'Not Recovered/Not Resolved' or 'Unknown' (Adverse Events): Leave it missing.
 - Completely missing and flagged as being ongoing (Prior/Concomitant Therapies and Medical/Surgical Procedures): Leave it missing.
 - Completely missing and with an outcome different from 'Not Recovered/Not Resolved' and 'Unknown' (Adverse Events): Impute to the date of end of participation.
 - Completely missing and not flagged as being ongoing (Prior/Concomitant Therapies and Medical/Surgical Procedures, Medical History Diseases): Impute to the date of end of participation.
 - Missing day and month: Impute to December 31st, unless year is the same as date of end of participation then impute to the date of end of participation.
 - Missing day: Impute to the last day of the month, unless year and month are the same as year and month of date of end of participation then impute to the date of end of participation.

4.2 Sample Size

The sample size calculation is planned to enroll enough subjects to enable the detection of treatment difference in the primary endpoint at Week 12. Approximately 84 subjects will be randomized in each nemolizumab group and in the placebo group for a total sample size of approximately 252 subjects.

Eighty-four (84) subjects per treatment group will have power $\geq 90\%$ to detect difference between placebo group (expected success proportion 20%) and nemolizumab group (30 mg or 60 mg, expected success proportion 50%) at the overall two-sided alpha of 0.05. A two-sided alpha of 0.025 will be spent for the comparison of each nemolizumab dose group versus placebo group.

4.3 Randomization, Stratification, and Blinding

Subjects will be centrally randomized using an Interactive Response Technology (IRT) system. Allocation concealment will be ensured, as the system will assign the randomization number only upon confirmation of eligibility for a given subject to participate in the study.

Subjects will be randomized in a 1:1:1 ratio to:

- Group 1: 30 mg Nemolizumab Q4W with 60 mg loading dose at baseline;
- Group 2: 60 mg Nemolizumab Q4W without loading dose at baseline;
- Group 3: Placebo Q4W.

Randomization will be stratified by clinical site.

The randomization code will remain blinded to all study sites and study team members until completion of the study and after the study database has been locked.

The IDMC will review data at periodic intervals throughout the study as defined in the IDMC charter. The IDMC charter will specify the procedures for unblinding to ensure that treatment assignment remains undisclosed to all individuals involved in the direct execution and management of the study until the final database is locked.

4.4 Multiplicity Adjustment for Primary and Key Secondary Efficacy Endpoints

In order to maintain the overall two-sided alpha of 0.05, a two-sided alpha of 0.025 will be spent for the comparison of each nemolizumab dose group versus placebo group. A predefined hierachal testing procedure will be implemented to test the primary and key secondary endpoints of each nemolizumab dose group versus placebo group.

The following hypothesis test will be evaluated for the primary endpoint at the two-sided alpha of 0.025:

$$\begin{cases} H_0: \pi_{Nemolizumab} = \pi_{Placebo} \\ H_a: \pi_{Nemolizumab} \neq \pi_{Placebo} \end{cases}$$

where $\pi_{Nemolizumab}$ is the proportion of subjects in nemolizumab group with an improvement of WI NRS ≥ 4 from baseline at Week 12 and $\pi_{Placebo}$ is the proportion of subjects in placebo group with an improvement of WI NRS ≥ 4 from baseline at Week 12.

The hypothesis tests for the key secondary efficacy endpoints are conditional on the success of the primary endpoint. The hypothesis tests for the key secondary efficacy endpoints will be evaluated on the ITT Set according to the following predefined order, all at the same two-sided alpha of 0.025, moving to the next hypothesis test only after a success on the previous hypothesis test. This approach does not inflate the type I error rate as long as the hypothesis tests for the key secondary efficacy endpoints are conditional on the success of the primary, there is a prospective specification of the testing sequence and no further testing is performed once the sequence breaks, that is, further testing stops as soon as there is a failure of a hypothesis test in the sequence to show significance at the predefined alpha level.

Key Secondary Efficacy Endpoints:

1. Proportion of subjects with an improvement of WI NRS ≥ 3 from baseline at Week 12.
2. Proportion of subjects with an improvement of WI NRS ≥ 4 from baseline at Week 4.
3. Proportion of subjects with an improvement of SD NRS ≥ 4 from baseline at Week 12.
4. Proportion of subjects with an improvement of WI NRS ≥ 3 from baseline at Week 4.
5. Proportion of subjects with an improvement of SD NRS ≥ 4 from baseline at Week 4.

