A summary based on observed case (OC) will be provided for all primary, secondary, and exploratory efficacy endpoints. At this case, no data will be imputed. For this summary, if any rescue medication is received or treatment is discontinued, and data are collected post-rescue receipt or treatment discontinuation, then the data post-rescue or post-discontinuation will be summarized as observed.

Proportion of subjects with WI NRS/SD NRS ≥ 4 and WI NRS ≥ 3 , changes and percent changes from baseline of WI NRS/SD NRS at each week (from week 1 through week 20) will be calculated on the basis of the weekly average, obtained by averaging at least 4 daily WI NRS/SD NRS scores over 7-day periods. If fewer than 4 daily WI NRS/SD NRS scores for the 7-day period (for baseline and week 12 wider periods apply) are available, weekly average WI NRS/SD NRS will be considered missing for that period. For the aim of sensitivity analyses, weekly averages of WI NRS obtained by averaging at least 3, 2 and 1 daily scores over 7-day periods will be calculated (no period extension at baseline and week 12 applies for these weekly averages). For detailed rules, refer to section 19.3.

Data of both nemolizumab groups (30 mg and 60 mg) and placebo group and comparisons versus placebo group of both nemolizumab groups will be presented.

Analysis of Primary Efficacy Endpoint

The proportion of subjects with an improvement of WI NRS ≥ 4 from baseline will be analyzed using the Cochran-Mantel-Haenszel (CMH) test stratified by analysis center; strata-adjusted difference in proportions between treatment groups and the 97.5% confidence interval (CI) of the difference will be based on the large sample approximation method for binary data.

Analysis of Key Secondary Efficacy Endpoints

The following key secondary efficacy endpoints will be analyzed using the Cochran-Mantel-Haenszel (CMH) test stratified by analysis center; strata-adjusted difference in proportions between treatment groups and the 97.5% confidence interval of the difference will be based on the large sample approximation method for binary data.

- Proportion of subjects with an improvement of WI NRS ≥ 3 from baseline at Week 12.
- Proportion of subjects with an improvement of WI NRS ≥ 4 from baseline at Week 4.
- Proportion of subjects with an improvement of SD NRS ≥ 4 from baseline at Week 12.
- Proportion of subjects with an improvement of WI NRS ≥ 3 from baseline at Week 4.

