- Proportion of subjects with an improvement of SD NRS ≥ 4 from baseline at Week 4.

1.0

CD14152.RD.06.SPR.204358 Protocol V06 21SEF

25-Sep-2023 00:00:00

Approved

Multiplicity Adjustment for Primary and Key Secondary Efficacy Endpoints

In order to maintain the overall two-sided alpha of 0.05, a two-sided alpha of 0.025 will be spent for the comparison of each Nemolizumab dose group versus placebo group. A predefined hierachal testing procedure will be implemented to test the primary and key secondary endpoints of each nemolizumab dose group versus placebo group.

Analysis Centers

Prior to database lock, a review of the blinded data will be performed to determine the size of each center. If there are centers with a small number of randomized subjects (i.e., centers with less than 12 randomized subjects), then these centers will be pooled in order for analyses to be carried out. The process of combining centers will be based on the ITT population, and same pooling will be repeated for mITT population and PP population.

Handling of Missing Data

Missing data for dichotomous efficacy endpoints will be imputed using multiple imputations (MI) under missing at random (MAR) assumption for the primary/main analyses. Dichotomous endpoints will be calculated from the underlying imputed variable.

For the sensitivity analyses of the primary endpoint, missing data will be imputed using a copy reference (CR) approach under missing not at random (MNAR) assumption

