The estimand for the primary endpoint will be analyzed using the Cochran-Mantel-Haenszel (CMH) test stratified by analysis center; strata-adjusted difference in proportions between treatment groups and the 97.5% confidence interval of the difference will be based on the large sample approximation method for binary data.

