9.1.1 Primary Analysis of the Primary Efficacy Endpoint (Estimand 1)

A summary will be provided for the primary efficacy endpoint without any imputation of missing data. Note that subjects who took rescue therapies at any point up to and including Week 12 are considered as treatment failures in this endpoint.

In the main statistical analysis described below, missing WI NRS weekly average values will be imputed for the ITT set using multiple imputations (MI) under missing at random (MAR) assumption. Worst values are assumed after use of rescue therapy or treatment discontinuation due to lack of efficacy or AE/death related to study drug prior to imputation. Dichotomous endpoints will be calculated from the underlying imputed variable. See [Appendix C](#) for details about Multiple Imputation.

The proportion of subjects with an improvement at Week 12 of WI NRS ≥ 4 from baseline without use of rescue therapies and without treatment discontinuation due to lack of efficacy or AE/death related to study drug will be analyzed in the ITT Set for each multiply imputed dataset, using the Cochran-Mantel-Haenszel (CMH) test stratified by analysis center; strata-adjusted difference in proportions between treatment groups (Nemolizumab – Placebo) and the 97.5% confidence interval (CI) of the difference will be based on the large sample approximation method for binary data using Mantel-Haenszel strata weights⁸ and the Sato variance estimator⁹. This analysis will be performed for both dosing schedules compared to placebo using the “Commonriskdiff” and “CL=MH” options in SAS PROC FREQ. Proportions and strata-adjusted difference in proportions will be pooled using Rubin’s method. Results from the CMH analysis will be combined using the Wilson-Hilferty transformation as described in the Bohdana Ratitch, et al. paper¹⁰ to produce a pooled CMH test p-value.

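### Optional improvement, not an error: a dose that wins all six of its tests could pass its 0.025 to the other dose, keeping family-wise error within 0.05 and losing no planned rejection; the gain is modest

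*SAP*

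**What the plan says.** SAP 4.4 sets an overall two-sided alpha of 0.05 and states that "a two-sided alpha of 0.025 will be spent for the comparison of each nemolizumab dose group versus placebo group". The primary hypothesis "will be evaluated for the primary endpoint at the two-sided alpha of 0.025". The five key secondary hypotheses follow in a fixed order, "all at the same two-sided alpha of 0.025", and "further testing stops as soon as there is a failure of a hypothesis test in the sequence to show significance at the predefined alpha level". Protocol 19.3.4 has the same procedure, and the protocol synopsis repeats the split: "a two-sided alpha of 0.025 will be spent for the comparison of each Nemolizumab dose group versus placebo group".

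The interval estimates follow the same level. The synopsis specifies "the 97.5% confidence interval (CI) of the difference", Protocol 19.3.1 specifies "the 97.5% confidence interval of the difference", and SAP 9.1.1 states that "the 97.5% confidence interval (CI) of the difference will be based on the large sample approximation method". The asterisk convention in SAP 4 also starts at p < 0.025.

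Neither document says what happens to a dose's 0.025 after all six of its hypotheses have been rejected.

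**The concern.** The procedure is two separate fixed sequences, each closed at 0.025. When one dose completes its sequence, its 0.025 has no further use. The other dose is still held to 0.025 and can miss a primary or key secondary claim with a p-value between 0.025 and 0.05, although the overall 0.05 would allow the claim. The trial compares two doses partly to choose between them (Protocol 19.6, SAP 15), so claims on the second dose have value.

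Four features keep the benefit small:

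- Transfer requires one dose to win all six tests.
- Three of the six are at Week 4, when both active arms have received the same 60 mg (SAP 3.1, 3.3). In the phase 2a study the Week 4 comparison was not statistically significant (Protocol 8.3.1).
- Two of the six are SD NRS responder tests. Inclusion criterion 5 sets a floor on WI NRS only, and a subject with baseline SD NRS below 4 cannot improve by 4.
- Transfer cannot change the chance of winning at least one primary, because it acts only after one dose has already won.

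**Working it through.** **Inputs from the documents.** 84 subjects per arm, 20% response on placebo and 50% on either dose (SAP 4.2); 0.025 per dose and six ordered tests per dose (SAP 4.4). Two-sided critical values are 2.241 at 0.025 and 1.960 at 0.05.

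**1. The plan's own power.** For 50% vs 20%:

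- pooled SE = √(0.35 × 0.65 × 2/84) = 0.0736, so z = 0.30/0.0736 = 4.08
- unpooled SE = √((0.25 + 0.16)/84) = 0.0699, so z = 4.29
- power at 0.025 = Φ[(0.30 − 2.241 × 0.0736)/0.0699] = Φ(1.93) = 97.3%

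The stated power of at least 90% is met.

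**2. Error control as planned.** Within a dose, the first true null in the sequence is tested at 0.025, so that dose makes a false rejection with probability at most 0.025. Over both doses the bound is 0.025 + 0.025 = 0.05.

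**3. Error control with transfer.**

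- If both doses contain a true null, neither can complete its sequence without first falsely rejecting a null of its own at 0.025. The first false rejection is therefore always made at 0.025, and the bound stays 0.025 + 0.025 = 0.05.
- If only one dose contains true nulls, its sequence is tested at 0.05 at most.

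Neither step uses the correlation between tests. This is a Bonferroni-based graphical procedure.

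**4. No planned rejection is lost.** Each dose starts at 0.025 and its level can only rise to 0.05. No critical value becomes stricter.

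**5. Ceiling on the gain for a primary.**

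- Planned effect: power at 0.05 is Φ[(0.30 − 1.960 × 0.0736)/0.0699] = 98.7%, so at most 98.7 − 97.3 = 1.4 points.
- Assumed weaker dose, 40% vs 20% (z = 0.20/√(0.30 × 0.70 × 2/84) = 2.83, rounded to 2.8): power is Φ(2.8 − 2.241) = 71.2% at 0.025 and Φ(2.8 − 1.960) = 80.0% at 0.05, so at most 8.8 points.

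The ceilings would be reached only if the other dose always completed its sequence.

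**6. Simulated gain.** The two sequences were simulated in SAP order with a shared placebo arm, 400,000 trials in each of 96 scenarios. Only 50% vs 20% comes from the documents. The assumptions are:

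- both Week 12 itch tests have that dose's primary z, taken as 4.1 (power 96.8% at 0.025) or 2.8;
- Week 4 itch power is equal in the two doses;
- SD NRS power is equal in both doses and both weeks, or the same as the itch tests of that week;
- endpoint correlation is 0.4, 0.6 or 0.8.

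No planned rejection was lost in any scenario. Gain in points on the weaker dose's primary at correlation 0.6, with the share of trials in which the strong dose completes its sequence in brackets:

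| Week 4 itch power | SD NRS 30% | SD NRS 50% | SD NRS 80% | SD NRS as itch |
|---|---|---|---|---|
| 30% | 0.4 (9%) | 0.7 (14%) | 0.9 (17%) | 0.6 (12%) |
| 50% | 0.7 (14%) | 1.3 (23%) | 2.1 (33%) | 1.7 (28%) |
| 80% | 0.9 (17%) | 2.1 (33%) | 4.3 (58%) | 4.7 (63%) |
| 97% | 0.9 (17%) | 2.3 (35%) | 5.3 (69%) | 7.5 (89%) |

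Over correlations 0.4 to 0.8 the range is 0.3 to 7.8 points.

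Sequence completion at Week 4 itch power 80%, plan then transfer:

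| SD NRS power | Weaker dose completes (40% vs 20%) | Both doses complete (50% vs 20% in each) |
|---|---|---|
| 30% | 16.0% → 18.2% | 6.5% → 11.1% |
| 50% | 29.6% → 34.1% | 17.6% → 26.2% |
| 80% | 46.8% → 54.1% | 41.4% → 53.6% |

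With 50% vs 20% in both doses, each primary gains 0.0 to 1.1 points from 96.8%, and at most about 0.2 if SD NRS power is 30 to 50%. The chance of winning at least one primary is unchanged: 97.7% with one weaker dose and 99.4% with two equal doses.

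**7. Simulated family-wise error** (1,000,000 trials each, Monte Carlo error 0.0002):

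| Setting | Plan | Transfer |
|---|---|---|
| Global null | 0.0466 | 0.0466 |
| One dose certain to complete, other null | 0.0250 | 0.0498 |
| One dose with itch power 80% and SD NRS power 30%, other null | 0.0252 | 0.0305 |

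**The case against.** The strongest reply is that nothing needs repair. An equal Bonferroni split with two independent sequences is valid, simple and a legitimate choice. At the only effect size in the documents the primaries gain almost nothing, and every larger figure rests on assumed inputs. This is correct, and it is why the point is offered as an option only.

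Other parts of the reply:

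- **The word modest does not fit every setting.** Fair in part. Completing both sequences can gain 12.2 points (41.4% to 53.6%). A separate patient-level simulation with a 36% vs 20% weaker dose and strong secondary effects in the other dose gave 8 to 9 points on the weaker primary. Modest describes the primaries when SD NRS power is 30 to 50%.
- **The phase 2a evidence is thin.** Fair. That study had 13 to 15 subjects per group, and Protocol 8.3.1 also reports post hoc Week 4 responder proportions above placebo in all nemolizumab groups. Week 4 power is therefore unknown, which is why it is varied from 30 to 97%.
- **A null second dose faces a doubled false-claim risk, and the doses may be judged at different levels.** True, but the risk stays within the 0.05 the plan already accepts, and no claim becomes harder to make.
- **The bound assumes valid p-values.** True of both procedures. With the pooled z-test at 20% response, the exact size is 0.0258 at nominal 0.025 and 0.0515 at nominal 0.05. This comes from the large-sample test, not the transfer. Centre-stratified CMH and multiple imputation were not modelled.
- **Supportive displays also depend on the level.** True of the tipping-point analysis and the forest plots. They need one aligning sentence.

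**Conclusion.** The point holds as an optional improvement. The planned procedure controls family-wise error at 0.05 and contains no error here. Adding transfer keeps that bound under any correlation, provided the individual p-values are valid, and retains every planned rejection.

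The size of the gain depends on secondary effects that the documents do not give. The likely benefit is a point or two on the primary of a weaker dose and several points on completing the second sequence. It is larger only if the Week 4 and SD NRS tests are well powered.

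**What to change.** If the sponsor wants the refinement, make these changes before unblinding:

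1. Add to SAP 4.4 and Protocol 19.3.4: *If all six hypotheses for one dose are rejected at two-sided 0.025, its alpha passes to the other dose, whose sequence is then tested in the same order at two-sided 0.05.*
2. In both sections, add *or 0.05 after transfer* to the sentences that fix the level at 0.025 for the primary and key secondary tests and to the stop-on-failure sentence.
3. Align the statistical methods text in the protocol synopsis.
4. Where 97.5% intervals are specified for the tested endpoints (synopsis, Protocol 19.3.1 and 19.3.2.1, SAP 9.1.1 and 9.2.1), add 95% intervals for any test made at 0.05.
5. Footnote the p < 0.025 asterisk rule in SAP 4.
6. State that the sensitivity and tipping-point analyses and the forest plots (SAP 9.1.2, 9.1.4, 9.2.2, 9.2.4) use the level at which that dose was tested.
7. Record the change in SAP 16, which now says the intent of the protocol text is unchanged.

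The sample-size text can stay, because 0.025 remains the starting allocation.

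The cost is text edits and an extra interval column, with no new data or analysis method. The documents do not settle whether a protocol amendment is needed. SAP 16 asks for one when blind review prompts a change to principal features, while Protocol 19 lets the SAP supersede the protocol. The sponsor should decide and document the reason. If the sponsor prefers the simpler split, no change is needed.
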